11.1.2 Disease Parameters

Measurable lesions are defined as those that can be accurately measured in at least one dimension (longest diameter to be recorded) as ≥ 20 mm with conventional techniques (CT, MRI, x-ray) or as ≥ 10 mm with CT scan. All tumor measurements must be recorded in millimeters (or decimal fractions of centimeters).

All other lesions (or sites of disease), including small lesions (longest diameter < 20 mm with conventional techniques) are considered non-measurable disease. Bone lesions, leptomeningeal disease, ascites, pleural/pericardial effusions, lymphangitis cutis/pulmonis, inflammatory breast disease, abdominal masses (not followed by CT or MRI) and cystic lesions are all non-measurable.

11.1.3 Methods for Evaluation of Measurable Disease

All measurable lesions that are not irradiated are identified as target lesions and recorded and measured by PET/CT or CT (chest/abdomen/pelvis) at baseline and at weeks 5 and 15. The abscopal response based on target lesions is defined in Table 2.

A sum of the longest diameter (LD) for all target lesions will be calculated and reported as the baseline sum LD. The baseline sum LD will be used as reference by which to characterize the objective tumor clinical response (definition in Table 2).

In parallel, assessment at PET scanning will be conducted. After at least a 4 hour fast, blood glucose will be checked. Patients will be injected with 10-15 mCi of F-18 FDG (fluoro-deoxy-glucose) in a resting state. After 45 minutes, whole body PET scans with attenuation correction will be performed from the cerebellum to the mid-thigh. Images will be corrected to provide standardized uptake values in g/ml. The Full Width Half Maximum of the scanner is approximately 4.6 mm. Therefore, we expect to be able to accurately assess lesions $>$ or equal to 1 cm in size. A qualitative assessment of lesions will be performed, i.e., visibility of lesion on F-18 FDG PET. In addition, the maximum standardized uptake value will be determined for each lesion. Criteria as described by the EORTC PET study group will be used to assess response based on standard uptake value (SUV) [82]:

Progressive metabolic disease:

Increase in SUV of more than 25%

Visible increase in the extent of FDG uptake $> 20\%$ in longest dimension

New metastatic lesions

Stable metabolic disease:

Increase in SUV of less than 25% or decrease of less than 15%

No visible increase in the extent of FDG uptake

Partial metabolic response:

Reduction in SUV between 15% and 25% after one cycle of treatment

Reduction in SUV of more than 25% after more than one cycle of treatment

Complete metabolic response:

Complete resolution of FDG uptake

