Secondary Endpoint: A. *to estimate the local response rate of combining TGF β receptor I kinase inhibitor LY2157299 and local radiotherapy,*

B. to determine if treatment with TGF β receptor I kinase inhibitor LY2157299 and localized RT enhances tumor-specific immunity in patients with metastatic breast cancer, and if this is associated with abscopal tumor regression.

C. to determine if treatment with TGF β receptor I kinase inhibitor LY2157299 and localized RT alters the numbers and function of T-reg cells in patients with metastatic breast cancer.

SCHEMA

Patients with metastatic breast cancer receiving at least one single agent chemotherapy and demonstrating stable disease or disease progression at two consecutive clinical/radiological assessments (at an interval of at least 2 weeks). Stable disease is defined as: < 30% decrease in the sum of the longest diameter (LD) of target lesions, taking as reference the baseline sum LD or < 20% increase in the sum of the LD of target lesions without the appearance of one or more new lesions. After obtaining informed consent:

Baseline CT and PET scan

Definition of target and non-target lesions: **Non-target** lesion is treated by radiation while **Target** lesions are followed to assess possible abscopal effect

[figure not shown]

TABLE OF CONTENTS

Protocol Summary	12
SCHEMA.....	14
1. STUDY OBJECTIVES	18
1.1. Primary Objectives.....	18
1.2. Secondary Objectives.....	18
2. BACKGROUND.....	18
2.1 TGF β.....	18
2.1.1 TGF β in Oncology: Rationale for Blocking TGF β signaling Therapy.....	20
2.2 Investigational Agent or Device	21
2.2.1 Pharmacokinetics and Pharmacology	21
2.2.2 Preclinical Studies	24
2.2.3 Toxicology Studies	24
2.2.4 Clinical Experience with LY2157299	25
2.3 Rationale	26
2.4 RT Dose Rationale	27
2.5 Risk/Benefit Assessment	27
2.6 Correlative Studies Background.....	28
2.6.1 TGF β gene response signature	28
2.6.2 Circulating levels of TGF β	28
2.6.3 Tumor-specific immune responses	28
2.6.4 Levels of circulating Tregs	29
3. SUBJECT SELECTION.....	29
3.1 Study Population.....	29
3.2 Inclusion Criteria.....	30
3.3 Exclusion Criteria.....	31
4 REGISTRATION PROCEDURES.....	33
4.1 General Guidelines	33
4.2 Patient Registration Process	33
5.1 Investigational Agent or Device Administration.....	34
5.2 Pretreatment Evaluations.....	34
5.3 On-Study Evaluations	35
5.4 General Concomitant Medication and Supportive Care Guidelines ...	37
5.5 Duration of Therapy	37
5.6 Duration of Follow Up.....	37

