11 MEASUREMENT OF EFFECT

Abscopal responses will be assessed at 15 weeks based on [78] (Table 2). This choice of this interval is to enable a sufficient length of study to detect abscopal responses. In fact, the experience in the clinical trials of Ipilimumab in melanoma demonstrated occasional initial progression of disease with appearance of new metastatic sites when compared to the baseline imaging assessment. “Flares” at the first PET/CT or CT(Chest/Abdomen/Pelvis) assessment were often followed by clinical responses to the antibody. While the mechanism of action of

Ipilimumab is different from that of LY2157299, the experience with TGF β inhibition in malignant glioma reported by Hau et al [79] confirms the lesson from the melanoma trials, i.e. that whenever the response is mediated by the immune system the following course is likely to manifest: 1) achievement of a clinical and radiological measurable response is slower than that of a typical response to cytotoxic therapy (RT or chemotherapy); 2) it can be heralded by an initial “flare” or emergence of new metastatic sites and, 3) with time it may be dramatic and would have been missed if the drug was discontinued too soon [80] [81].

Table 2: Immune response criteria (irRC)

	Summary of irRC
Note:	New, measurable lesions are incorporated into tumor burden
CR	Disappearance of all index and non-index lesions in two consecutive observations not less than 4 weeks apart, without the development of any new lesions.
PR	$\geq 50\%$ decrease in tumor burden compared with baseline in two observations at least 4 weeks apart
SD	50% decrease in tumor burden compared with baseline cannot be established nor 25% increase compared with nadir
PD	At least 25% increase in tumor burden compared with nadir (at any single time point) in two consecutive observations at least 4 weeks apart

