11.1 Anti-tumor Effect

11.1.1 Definitions

Patients will be evaluated by PET/CT or CT(chest/abdomen/pelvis) at baseline, week 5 and week 15. However, systemic anti-tumor response will be by PET/CT or CT(chest/abdomen/pelvis) as defined by irRC at 15 weeks (primary endpoint).

Patients who have received at least one 14 days cycle of the study drug will be followed for toxicity (lack of grade 4 toxicity— primary safety end point). Patients will receive a total of 14 doses of LY2157299 (one dose daily for 14 consecutive days), per cycle. Patients who have received any treatment will also be evaluated for abscopal response to the metastatic sites using the immunologic response criteria based on the 5 and 15 week PET/CT or CT(chest/abdomen/pelvis) scans as outlined above in Table 2.

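### Table 2 sets the 50%/25% response cut-offs on a tumor burden with no unit, and section 11.1.3 supplies only a sum of longest diameters, so the primary abscopal endpoint may be stricter than the one the trial was sized for

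*Combined protocol and SAP*

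**What the plan says.** Section 11.1.1 takes systemic response "as defined by irRC at 15 weeks (primary endpoint". Section 11.1.3 sends the reader to the same criteria: "The abscopal response based on target lesions is defined in Table 2".

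Table 2 (section 11) defines partial response as a fall in tumor burden of at least 50% from baseline and progression as a rise of at least 25% from nadir. Stable disease is what lies between: "50% decrease in tumor burden compared with baseline cannot be established nor 25% increase compared with nadir". The table notes that "New, measurable lesions are incorporated into tumor burden", but does not say whether burden is a length, an area or a volume.

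The only scale comes from sections 11.1.2 and 11.1.3. Section 11.1.2 asks for the longest diameter of each measurable lesion. Section 11.1.3 says "A sum of the longest diameter (LD) for all target lesions will be calculated and reported as the baseline sum LD", and then "The baseline sum LD will be used as reference by which to characterize the objective tumor clinical response (definition in Table 2". No second diameter, product of diameters or volume is defined for target lesions.

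The schema also uses sum LD, for disease status at study entry: "Stable disease is defined as: < 30% decrease in the sum of the longest diameter (LD) of target lesions", or a rise of less than 20% with no new lesion.

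**The concern.** On one measure, sum LD, the protocol draws its lines at 30%/20% in the schema and, read literally, at 50%/25% in the primary endpoint. The gap in the decrease cut-off is about what would arise if the 50% had been set for an area and then attached to a sum of diameters.

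The scale decides who counts as a responder. Under Sample Size, the combination is rejected with 3 or fewer responses in 28, so reclassifying one or two patients can reverse the conclusion. The 5% and 19% rates behind the design are given for the immune response criteria, without the scale on which those criteria are scored. If the scale stays open until review, two readers could also grade the same scans differently.

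**Working it through.** **Inputs.** From Sample Size: n = 28, null rate 0.05, alternative 0.19, alpha 0.05, power 80%, rejection at 3 or fewer responses. From Table 2: 50% and 25%. From the schema: 30% and 20% of sum LD.

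**1. The plan's own design.** With X binomial(28, p), the combination goes forward if X ≥ 4.
- P(X ≥ 4 | p = 0.05) = 0.0491, within the nominal 0.05.
- P(X ≥ 4 | p = 0.19) = 0.8065, against 80% stated.

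The design reproduces. The sample-size arithmetic is not in question.

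**2. Converting between scales.** Assume every lesion changes in the same proportion, so that area factor = (LD factor)².

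| Change | LD factor | Area factor | Change in area |
|---|---|---|---|
| 50% fall in LD (Table 2, literal) | 0.50 | 0.25 | 75% fall |
| 30% fall in LD (schema) | 0.70 | 0.49 | 51% fall |
| 25% rise in LD (Table 2, literal) | 1.25 | 1.5625 | 56% rise |
| 20% rise in LD (schema) | 1.20 | 1.44 | 44% rise |

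In reverse, a 50% fall in area is an LD fall of 1 − √0.5 = 29.3%, and a 25% rise in area is an LD rise of √1.25 − 1 = 11.8%.

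The literal response line thus asks for 50/30 = 1.7 times the diameter shrinkage of the schema's line. A 50% area cut-off would almost coincide with the schema's 30%. The increase cut-offs do not coincide: 11.8% against 20%.

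**3. Effect on power.** Suppose 19% was meant on an area-type scale but responses are scored at a 50% fall in sum LD. Let f be the share of intended responders who also reach that fall. The documents give no value for f, so a range is shown. The response rate becomes 0.19f, and the null rate 0.05f if it scales in the same way.

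| f | 0.19f | Power, P(X ≥ 4) | Type I error at 0.05f |
|---|---|---|---|
| 1.0 | 0.190 | 0.81 | 0.049 |
| 0.9 | 0.171 | 0.73 | 0.035 |
| 0.75 | 0.1425 | 0.58 | 0.020 |
| 0.5 | 0.095 | 0.27 | 0.005 |

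Power and type I error fall together, so a mismatch in this direction makes the trial miss an effect. It does not produce false positives.

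**The case against.** **The schema does not contradict Table 2.** A reader might infer that the protocol gives two conflicting cut-offs for one endpoint. It does not. The schema classifies disease at entry, after earlier therapy. Table 2 grades response at week 15 against the trial baseline. Nothing requires the two to match, and the text can be applied as written. This objection stands.

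**The area reading reconciles only half of the pair.** It brings the decrease cut-offs together, but 25% of area is an 11.8% rise in LD, farther from the schema's 20% than a literal 25% is. This also stands. The documents alone do not establish that area was intended. Reference 78, which section 11 cites as the basis, would have to settle it.

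**Sum LD is not always the stricter scale.** The conversion needs proportional change, while section 11.1.3 sums all measurable lesions that are not irradiated. Take illustrative lesions of 60, 20, 20 and 20 mm, and let the three small ones disappear. Sum LD goes from 120 to 60, a 50% fall. Area, in units of LD², goes from 3600 + 3 × 400 = 4800 to 3600, a 25% fall. That patient responds on LD but not on area. The point is valid, and it means the scale can move patients in either direction.

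**The loss of power cannot be sized from the documents.** A reader might assume normally distributed change in sum LD with an SD of 20 to 40 points, place the 19% at a 29.3% fall, and conclude that power is only 1% to 19%. No section supports that distribution or SD, and the range omits milder cases. Complete response does not depend on the scale, and section 11 expects that immune responses can be dramatic. Both favor a higher f.

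What remains is that burden has no stated unit, the only scale offered is a length, and the design rates are not tied to a scale.

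**Conclusion.** The point holds as an undefined scale for the primary endpoint, with a literal reading that may be stricter than intended. As written, a partial response needs a 50% fall in sum LD, which is 75% in area under proportional shrinkage. The schema's 30% suggests that the 50% cut-off belongs to an area scale, but does not prove it.

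If 5% and 19% are already rates on sum LD, nothing is lost: alpha is 0.049 and power 0.807. If they are rates on an area scale, power is below the stated 80% in each case tabulated with f below 1, from 0.73 at f = 0.9 to 0.27 at f = 0.5. These figures rest on an assumed f. The documents do not support the claim that the endpoint is certainly too strict, or any single figure for the loss.

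It should be settled because the scale determines the count behind the go/no-go rule.

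**What to change.** Before response review:

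- Check the criteria cited as reference 78, and define tumor burden once, consistently across Table 2 and sections 11.1.2 and 11.1.3, on the scale for which 50% and 25% were set. If that is the sum of products of perpendicular diameters, record the second diameter on existing scans and replace sum LD in section 11.1.3. Put new measurable lesions on the same scale, since Table 2 adds them to burden while section 11.1.3 sums target lesions only.
- State under Sample Size that 5% and 19% are rates on that scale. If they are, n = 28 and the 4-response rule stand unchanged.
- Report response on the other scale as a sensitivity analysis.

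Do not move the schema's 30%/20% into Table 2 by default. It is an entry definition, and an easier cut-off carries the opposite risk. If 5% was a rate for a 50% LD fall and the null rate on the easier scale were 10% (an assumption), P(X ≥ 4 of 28) under the null would be 0.31.

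The cost is wording and, at most, one extra diameter per target lesion on scans already taken.

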11.1.4 Response Criteria

11.1.4.1 Evaluation of Target Lesions

Criteria for evaluation of response are reported in Table 2.

11.1.4.2 Evaluation of Non-Target Lesions (irradiated Lesions)

Complete Response (CR): Disappearance of all non-target lesions and normalization of tumor marker level

Incomplete Response/
Stable Disease (SD): Persistence of one or more non-target lesion(s) or/and maintenance of tumor marker level above the normal limits

Progressive Disease (PD): Appearance of one or more new lesions and/or unequivocal progression of existing non-target lesions

Although a clear progression of “non-target” lesions only is exceptional, in such circumstances, the opinion of the treating physician should prevail, and the progression status should be confirmed at a later time by the review panel (or study chair).

Note: If tumor markers are initially above the upper normal limit, they must normalize for a patient to be considered in complete clinical response.

11.1.4.3. Evaluation of Best Overall Response

The best overall clinical response is the best clinical response recorded from the start of the treatment until disease progression/recurrence (taking as reference for progression disease the smallest measurements recorded since the treatment started). The patient's best response assignment will depend on the achievement of both measurement and confirmation criteria (see section 12.1.4.4 below).

Notes: Patients with a global deterioration of health status requiring discontinuation of treatment without objective evidence of disease progression at that time should be classified as having

“symptomatic deterioration”. Every effort should be made to document the objective progression, even after discontinuation of treatment.

In some circumstances, it may be difficult to distinguish residual disease from normal tissue. When the evaluation of complete response depends on this determination, it is recommended that the residual lesion be investigated (fine needle aspirate/biopsy) before confirming the complete response status.

11.1.4.4 Confirmation Criteria

To be assigned a status of PR or CR, changes in tumor measurements must be confirmed by repeat assessments that should be performed after a minimum of 4 weeks, no less, after the criteria for response are first met.

11.1.5 Response Review

All responses will be reviewed by an expert(s) independent of the study at the study's completion.

12 DATA REPORTING/ REGULATORY CONSIDERATIONS

The WCM Data and Safety Monitoring Committee (DSMC) is the central monitoring board for this study. The UCLA Cancer Institute Data and Safety Monitoring Committee (DSMC) is the local monitoring board for UCLA patients. [name]. is the Co-Chairman of the Cancer Clinical Trials at the WCM Data Safety Monitoring Committee. He will also serve in the capacity of the Independent Research Monitor.

The Research Monitor, [name], is responsible to oversee the safety of the research and report observations/findings to the IRB or a designated institutional official. The Research Monitor will review all unanticipated problems involving risks to subjects or others associated with the protocol and provide an independent report of the event to the IRB. The Research Monitor may discuss the research protocol with the investigators; shall have authority to stop a research protocol in progress, remove individual human subjects from a research protocol, and take whatever steps are necessary to protect the safety and well-being of human subjects until the IRB can assess the monitor's report; and shall have the

responsibility to promptly report their observations and findings to the IRB or other designated official and the HRPO.

12.1 Monitoring plan

This study will be conducted in accordance with the guidelines in the 2001 NCI approved data Safety and Monitoring plan for the WCM Cancer Institute and with the UCLA approved data Safety and Monitoring plan for the UCLA Cancer Institute. Reports to the Data Safety and Monitoring Committee will include the following information: accruals, targets, responses, adverse events and evidence of reporting to appropriate review committees. The WCM Data and Safety Monitoring Board (DSMB) will review the IRB approved protocol, the data and safety monitoring plan and any stopping guidelines during protocol initiation. The WCM DSMB is to perform a data and safety analysis annually (as per DSMB letter dated 04.20.2017) following the accrual of the first subject. . The WCM DSMB may also convene as needed if stopping criteria are met or other safety issues arise that the Principal Investigator and/or IRB would like the WCM DSMB to address.

As per WCM DSMB recommendations, the safety analysis will be performed annually, at which point the protocol and safety analysis should be submitted to the DSMB for review.

12.2 Stopping rules (for the individual patient and for the study as a whole)

Patients will be discontinued from study therapy when any clinical adverse event greater than Grade 3 or intercurrent illness in the opinion of the Principal Investigator, indicates that continued treatment with the study therapy is not in the best interest of the subject. Patients will be monitored until the resolution of the adverse event. Based on PI's discretion, patients will resume or will be withdrawn from the study therapy.

If five or more non-hematological toxicities, Grade 3 and above, are reported over a period of 3 months, will result in temporary discontinuation of combination therapy.

12.3 Data Management

All patient data will be entered and maintained using REDCAP, CTSC data management system. These data include clinical data and all patient safety data. The REDCap provides audit trails that track creation and modification of records that include user id and timestamp. Depending on the database account privileges, the data managers may be able to correct a discrepancy or if not, route it to the project data manager at WCM who can take appropriate action to correct the problem. Data clarification forms can also be printed out when necessary to be sent to the project data manager at JCTO.

The Nurse practitioner will also be documenting adverse events in EPIC during every follow up visit, All Adverse Events are captured in REDCap database and a report will be sent to Data safety monitoring board during their quarterly review meetings.

All key end points will be source verified by a second person at each site and errors will be corrected. Once the data is verified and all discrepancies are closed, the data can be locked/frozen. Locking and freezing can be done at different granular levels and will follow institutional SOPs and any specific requirements for the project.

Security measures that will be taken in order to protect patient data will include firewall technology and database level security which will be achieved by assigning roles and privileges to different levels of users and by requiring that the users authenticate themselves using user id and password. Additional security for data transfer between remote clients and servers will be achieved by using digital certificates/SSL. All data will be backed-up to tape periodically according to the Institutional SOPs. All data will be stored for at least 5 years following the termination of this study.

12.4 Confidentiality

The medical, hospital and research records associated with this study are considered confidential. Members of the treating team and designated study assistants will have access to the records as required to administer treatment and comply with the protocol. Neither the name nor any other identifying information for an individual will be used for reporting or publication regarding this study. All laboratory and baseline data will be de-identified and transferred via secure links to the database at WCM. Patient records will be made available for inspection to auditing agencies to satisfy regulatory requirements. Privacy will be maintained throughout the consent process and protocol treatment.

